## 2.1.3.8 Effect of the Location of the Infarct Vessel

In the reperfusion era, measures of left ventricular function, heart failure, and age have been consistently related to 6-12 month mortality and development of heart failure. However, we now know that the location of the infarct vessel is an important determinant of morbidity and mortality rates. It is of interest to assess whether the location of the infarct vessel influences the effect of time on the role of cell therapy on the study endpoints.

## 2.1.4 Summary of rationale

The established safety record, relative ease of cell acquisition and preparation of BMMNC coupled with the positive findings published by several groups (8-10, 20) have

prompted many clinical sites throughout the world to embark in developing this therapy for their patients with AMI. However, the CCTRN believes that widespread adoption of this therapy is premature given the methodological limitations present in the previous trials. These include the following: 1) Failure to randomize or include a true placebo group, 2) Use of left-ventriculography for calculations of the primary endpoint (LVEF), 3) Patient populations with ejection fractions frequently greater than 50% who are unlikely to develop significant left ventricular dysfunction, 4) Failure to give a uniform dose of BMMNC within each study, 5) Significant target vessel revascularization due to the exclusive use of BMSs and 6) Failure to pre-specify the timing of administration of cells following MI.

To address the above limitations we have proposed a randomized, blinded, placebocontrolled, clinical study of autologous BMMNC administration to 120 patients following AMI. To further evaluate the potential efficacy of this therapy, enrollment will be limited to patients with moderate to large infarctions with no prior history of CABG and whose ejection fraction following revascularization is <45%. The primary end-point of the study will be change in regional and global LV function (LVEF) at six months compared to baseline as measured by cMRI. Patients will be followed for two years to evaluate the effect of this therapy on clinical end-points such as death, repeat revascularization, MI and hospitalization for HF. Patients will be randomized in a 2:1 ratio of stem cell treatment to placebo. Because the important question of timing of cell delivery post-MI has never been addressed in any clinical study, the patients will be randomized to cell therapy at two physiologically distinct time points. Additionally, this will be the first clinical trial to administer the same dose of cells to all patients. To accomplish this we will administer 150 x 10^6 TNCs (70-80% BMMNC) to all patients at the pre-specified times of three versus seven days post-MI. It is the intention of this Phase II study to establish time points for delivery of BMMNC following MI that potentially can be used as the basis for a larger clinical Phase III study using either BMMNC or a more enriched cell type such as CD34+. A secondary goal of this trial will involve the establishment of a biorepository to examine how cell phenotype (cytokine and nitric oxide production, etc.) may affect therapeutic efficacy.

## 2.2 Preliminary studies to support the protocol

## 2.2.1 Ongoing feasibility study

To support the rationale and safety of this trial a pilot study was initiated in December 2005 following Investigational New Drug (IND) approval by the Food and Drug Administration (FDA) (BB-IND #12480) in September 2005 at the Minneapolis Heart Institute and Abbott Northwestern Hospital.

A total of 40 patients have been enrolled. All patients presented with an AMI and underwent successful percutaneous revascularization of the LAD coronary artery as part of the *Level 1 AMI* program developed at the center (35). Entry criteria included the requirement that LVEF was <50% as measured by left-ventriculography or echocardiography. All patients underwent cMRI studies prior to receiving cell therapy. Following informed consent, the patients underwent bone-marrow aspiration (50-70 ml) under local anesthesia at the posterior iliac crest in the morning of the study. Patients are randomized in a 3:1 ratio of cell therapy to placebo. All patients underwent bone marrow aspiration and intracoronary infusion of BMMNC (100 x  $10^6$  cells TNC) or placebo (5% albumin in normal saline (NS)).

The day of stem cell infusion was determined by the patient's clinical course, with administration of the cellular product occurring towards the end of their expected hospitalization (three to eleven days, mean=5.2 days). The aspirate was transported to the University of Minnesota Cell Therapy Lab, an FDA approved, GMP facility where the mononuclear cells were isolated by FicoII density centrifugation. The cells were transported back to the hospital in the afternoon following checks for sterility, and viability measurements in sterile, labeled bags containing 100 million BMMNC in 5% human albumin solution.

The patients were transferred to the cardiac catheterization laboratory in the afternoon for infusion of the cellular product. Following placement of a 6 French (Fr) sheath in the right femoral artery, angiography is performed to document patency of the stented artery. The patient is given 3000U of heparin (iv) and a 3.5 Fr infusion catheter (*Tracker, Boston Scientific*) was advanced over a guidewire and placed at the distal end of the stented segment. A total of 100 million BMMNC's are infused over 20 minutes by hand injection at a rate of 5 million cells per minute. Following completion of the infusion, a final angiogram is taken of the artery to document patency and TIMI 3 flow. All patients were routinely discharged the following day.

#### 2.2.1.1 Preliminary Results

Forty patients (31M, 9F) with moderate to large anterior infarctions have enrolled in the trial to date. Their average age is 54 years and seven have non-insulin dependent diabetes mellitus (NIDDM). Their average ischemic time is 7.2 hrs and seven have required intra-aortic balloon pump (IABP) support. Two patients underwent hypothermia treatment following initial cardiac arrest. The average day of transplant was five ± two days following their MI. The peak creatine kinase (CK) was 3074 IU and the CKMB was 282 IU. Their average LVEF by echocardiography performed one day following their MI was 37%. Their average LVEF by cMRI was 48% performed three to five days following their MI. In the Minneapolis Heart Institute, the LVEF by cMRI is 10% higher than that measured by echocardiography. All patients had significant MVO on their baseline MRIs. Their average LVEDV was 189.5 ml and left ventricular end systolic volume (LVESV) was 102.9 ml with an initial LV mass of 173 grams.

The average bone marrow aspirate collection was 65 ml and the mean BMMNC number was 170 million cells. The average percent  $CD34^+$ ,  $CD133^+$  and  $CD34^+/CD133^+$  cell TNC count in the delivered cell product was 2.01%, 0.22% and 1.09% respectively. The viability of the isolated BMMNC was greater than 96% in all patients.

Four significant adverse events were reported during the trial. One patient in the placebo group received an ICD for palpitations and syncope. One patient in the BMC group underwent CABG 8 months following cell therapy for an anomalous right coronary artery that was found to course between the aorta and pulmonary artery. One patient in the placebo group underwent repeat stenting in the LAD for in-stent restenosis at 15 months followed by CABG one month later after admission for a NSTEMI due to stent thrombosis. One patient in the BMC group underwent stenting of the circumflex artery two months following cell therapy infusion due to a pre-existing stenosis. There were no serious, unexpected, events that were related or possibly related to the study product or procedure reported during the trial.

## 2.2.2.2 Complications and Adverse Events (AEs)

There have been no complications associated with the bone marrow aspiration or stem cell infusion. There has been no quality issues associated with the cellular product. There have been three AEs, none attributed to the intervention. One patient was readmitted overnight, one month following his stem cell infusion with chest pain. The cause of pain was determined to be gastrointestinal. One patient underwent repeat revascularization of the target vessel at four months due to the presence of stenosis proximal to the LAD stent. This was successfully treated with the placement of a second DES and he was discharged the following day. There have been no arrhythmias detected by serial Holter monitoring in any of the patients although one patient received an implantable cardiac defibrillator (ICD) three months following cell administration because of the development of palpitations and light-headedness. No ventricular arrhythmias were ever documented in the patient.

## 2.2.3 Cell Isolation

To address variation in cell preparation techniques, the CCTRN proposes to utilize a closed cell separation system (Sepax, *BioSafe*) that will provide for ease of utility among network sites and reproducible product generation. In order to demonstrate comparability of the Sepax density gradient cellular product with that of traditional open systems (Manual density gradient), a series of experiments were performed doing direct comparison, which are fully described in a separate document. Briefly, bone marrow aspirations (100ml) were obtained from normal donors and split between the two systems. The final product from each method was compared to the starting population with regards to total nucleated cells (TNC), mononuclear cells (MNC), CD34+ cells and Colony Forming Units (CFU) recovery. Results are summarized in Table 2a.

	Starting TNC (x10  )	TNC Recovery (%±SD)	MNC Recovery (%±SD)*	CD34+ Cell Recovery (%±SD)
n=12				
Manual	10.3±4.7	24.1±6.6	46.8±16.4	64.6±16.7
Sepax	13.9±3.7	19.5±4.4	46.5±16.2*	68.3±12.2

 Table 2a. Sepax versus Manual Comparison Results

\* n=6 only due to an attempt to reduce the wash volume from 50 ml to 30 ml and obtain the cells in the 30 ml final volume needed for the trial.

In addition, flow cytometric analysis on the final cellular products demonstrated that there was not a preferential enrichment of a particular subpopulation by one procedure compared to the other. Finally, cells were incubated overnight in X-VIVO-10 media as

previously described by Seeger et al. (25). We did not see a significant difference in the cells obtained from either the manual or Sepax procedure after this culture period

## 2.2.4 Catheter compatibility

Three samples of bone marrow cells were passed through a PTCA catheter (*Maverick*, Boston Scientific). Fractions were collected and analyzed to determine if there are any adverse affects on the cells. The mononuclear cell fraction was enriched from three bone marrow samples using the Sepax device and a density gradient solution (GE Healthcare). The enriched cells were resuspended in a 30 ml sample (5% Albumin/PBS) and then passed through the catheter. Six fractions (each approximately 5 ml) were collected for analysis. Bone marrow was harvested from normal donors (*Cambrex*, Maryland) and shipped to MDACC overnight. The diameters of the three catheters were 2.5 mm, 3.0 mm, and 3.5 mm. Samples were submitted from each fraction for total nucleated cell counts (TNC) and viability determination (7-AAD, Flow Cytornetry)

(Total nucleated cell counts = cell concentration x cell volume; Cell Recovery = Absolute cell number post-processing in each fraction/Absolute cell number pre-processing in each fraction; Total Cell Recovery = Total cells recovered after processing/Total cells pre-processing). The final fraction was submitted for 14-day sterility cultures, and a pooled sample from the fractions was submitted for CFU assay. Detailed numbers will be provided in a separate document, but the following conclusions were found:

- Individual TNC recovery was >60% for all fractions in each run
- Overall TNC recovery was 83% for each run
- Viability was >95% for all fractions in each run
- Sterility was negative for each run (based upon evaluation of the final fraction passed through the catheter)
- CFUs for each run demonstrated growth (based upon a pooled sample)
- Overall recovery of CFU was >96%

All expected outcomes were met for all three runs. Based upon these data, it has been concluded that there is no adverse effect on mononuclear cell-enriched bone marrow cells by passing them through the catheter.

## 3.0 STUDY DESIGN

## 3.1 Introduction

To answer the aforementioned questions of cell dose and timing; we propose a randomized, double-blinded, placebo-controlled, clinical trial of a single dose of autologous BMMNC administration to patients following acute MI. Patients will be recruited to this protocol following intervention for AMI and assessment of LV function.

Enrollment in each treatment arm will be limited to patients with moderate to large infarctions with no prior history of CABG or MI that resulted in LV dysfunction and whose initial ejection fraction measured by echocardiography is  $\leq$  45%.

## 3.2 Objectives

The clinical hypotheses of TIME are that BMMNC cell administration post-MI improves clinically important measures of LV function and that the timing of BMMNC administration influences the magnitude of this effect.

## 3.2.1 Specific Objectives

The specific objectives of TIME are:

- 1. To evaluate the effect of a single intracoronary infusion of autologous BMMNC on regional and global LV function when compared to placebo in patients with an acute MI as assessed by cMRI.
- 2. To assess whether the effect of this BMMNC infusion on regional and global LV function is influenced by whether it is given at three versus seven days post-MI.

These objectives will be addressed by a randomized, double-blinded, placebocontrolled, 2x2 factorial clinical trial.

## **3.2.2 Primary Endpoints**

There are two co-primary endpoints for this study: 1) change in global LV function from baseline to six months in the active group as compared to the analogous change in the control group, 2) change in regional LV function from baseline to six months in the active group compared to the change in the control group. Each will be measured by cMRI, which is expected to be available on almost all patients.

## 3.2.3 Secondary Analyses

The interaction of the effect of therapy and timing of administration will be examined with each of the following secondary endpoints.

- Combined endpoint (first of) death, reinfarction, repeat revascularization, hospitalization for HF
- All patients will be followed for overall survival
- LV mass
- LVEDV
- LVESV
- Infarct size

## 3.2.4 Intervention

Active therapy consists of approximately  $150 \times 10^6$  TNC (80% BMMNC). This dose was chosen based on our ability to consistently obtain at least 150 million cells with a 80-90 ml bone marrow aspirate using local anesthesia in a pilot study of 40 patients enrolled to date. Only one bone marrow aspiration will be attempted.

Placebo patients will undergo bone marrow aspiration of the same volume, but receive only 5% human serum albumin/saline. Randomization will be a 2:1 (active:placebo) allocation.

#### 3.2.5 Stratification

Patients will be stratified by Clinical Center.

#### 3.2.6 Sample size

The trial is a 2 x 2 factorial design (Table 3). The two factors are therapy (active versus placebo) and timing (three days versus seven days). Patients will be allocated in a 2:1 treatment versus placebo ratio at each of the two time points.

 Table 3. Cell Delivery and Timing

	Timing				
Placebo	3 Days	7 Days			
Active	3 Days	7 Days			

The questions this study is designed to answer are:

- 1. What is the effect of stem cell therapy on global and regional LV function when compared to placebo?
- 2. What is the influence of three day versus seven day cell delivery on the effect of BMMNC on global and regional LV function?

A total of 120 patients provide adequate power for an assessment of the overall effect of BMMNC administration to control in the six month change for each of global and regional ejection fraction, as well as permitting an adequately powered inquiry into the influence of timing on the effect of BMMNC for each co-primary endpoint (Table 4).

	Global	LVEF	Regiona	al LVEF
	Tim	ning	Tim	ning
Active	3 Days 40	7 Days 40	3 Days 40	7 Days 40
Placebo	40 20	40 20	20	40 20
1 lacebo	20	20	20	20

Table 4. Total sample size for global and regional LVEF

#### 3.2.6.1 Assumptions

In the absence of efficacy monitoring by the DSMB, hypothesis testing for the primary endpoint(s) will be carried out at the 0.05 level. Assuming independence and normality of the observations, the sample size is calculated using the normal approximation to the two sample *t*-test statistic

$$N = \frac{\left(k+1\right)\sigma_{\Delta}^{2}\left(\frac{k+1}{k}\right)\left[Z_{1-\alpha/2} - Z_{\beta}\right]^{2}}{\left(1-f\right)\delta^{2}}$$
(1)

where

January 25, 2010

- N = number of placebo patients + number of active group patients
- $\alpha$  = Type I error
- $\beta$  = Type II error
- $Z_c$  = the  $c^{th}$  percentile from the standard normal probability distribution
- $\delta$  = effect size (i.e., difference between the change in the active group over time minus the change in the control group over time
- $\sigma_{\Delta}^2$  = variance in the change over time (incorporates the correlation over time). This variance is pooled between the active and placebo groups.
- k = ratio of number of active group to placebo group patients.
- f = expected proportion of patients anticipated to be lost to follow-up.

In the analysis, the first examination will be the effect of cells on the co-primary endpoints, followed by an assessment of the influence of cell timing delivery on the relationship between cell therapy and the co-primary endpoints. Overall efficacy will be evaluated by comparing treatment versus control together. A sample size of 120 patients is required

## 3.2.6.1.1 Global ejection fraction assumptions

Assume an absolute change  $\delta = 5$  and common group standard deviation of the difference of LVEF over time as  $\sigma(\Delta)_{LVEF} = 7$ , as reported in the Wollert (24), Lunde (16), Schächinger (19), and Janssens (15) articles.

## 3.2.6.1.2 Regional ejection fraction assumptions

Assume an absolute change  $\delta = 6.7$  and a common group standard deviation  $\sigma_{rLVEF} = 9.5$ , from the 2004 Boost manuscript (18,24).

## 3.2.6.2 Sample size for cell delivery timing effect

The specific aim is the determination of the influence of timing on the effect (on each coprimary endpoint) produced by the BMMNC administration. Patients are randomly allocated to BMMNC at three days or seven days and followed for six months and with the change in both global and regional ejection fraction measured. Control group patients receive placebo when randomized to either three or seven day administration.

Under either the null hypothesis (of no BMMNC effect over the duration of the study), or the alternative hypothesis (BMMNC effect over the duration of the study), there will be no difference in the response of the control group to either day three or day seven placebo administration. Thus, an evaluation of the effect of timing on either global or regional ejection fraction involves a comparison of the response of the seven day administration active group to the three day administration active group.

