#### 2.1.3.2 Effect of timing of cell administration

Although the timing of administration of cell therapy following MI may be a critical factor in dictating efficacy, this property of the intervention has never been directly addressed in a clinical study. The early inflammatory milieu and presence of MVO present in the first few days following an MI may create an adverse environment for delivery and survival of transplanted cells, which may have contributed to the negative findings of clinical studies that administered cells within one day following MI (16). Conversely, certain stem cell homing factors such as SDF-1 are elevated in the early post-infarction period (11, 21) that could benefit stem cell retention. In the mouse, myocardial expression of SDF-1, VEGF and hepatocyte growth factor (HGF) are maximally up-regulated at 48 hours post-MI and decline significantly by 96 hours following MI (22).

In a pre-clinical model, Ma et al.(21) administered 5 x  $10^6$  MSC via the tail vein in rats at multiple time-points post-MI (12hrs, 1, 2, 4, 8, 16 days). They observed that the greatest number of labeled MSC retained in the heart when measured three days following administration occurred in those animals that received cells one day post-MI. The number of retained cells declined significantly with each subsequent day of administration such that no cells were present when cell administration occurred at eight or sixteen days post-MI. Cell retention was highly correlated with improvement in fractional shortening and vessel density in the peri-infarct region. Unfortunately, no pre-clinical data have been published that has examined the effect of timing of stem cell administration post-MI in a larger animal model where the inflammatory and healing response may be significantly different (23).

In the previously published randomized clinical trials (16, 17, 20, 24), BMMNC were administered between one and seven days but timing was never integrated into the randomization scheme (Table 2). Thus, the effect of timing of administration of BMMNC following AMI is not known. This will be the first trial to randomize the timing of administration to an early (three days post-MI) or middle (seven days post-MI) time point. The potential benefit of cell administration several weeks following MI will be investigated in a second trial (Late-TIME).

Study	Total Cells (x 10  )	CD34 + (x 10  )	Outcome

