## 3.2.6.2.1 Effect of timing of delivery on global ejection fraction

Evaluation of the influence of timing on global ejection fraction involves comparing the effect of BMMNC at the day three administration to the effect of BMMNC at the seven day administration. Assume the difference in the treatment effect is  $\delta = 5$ . The standard deviation of the change in ejection fraction from baseline to six months is 7.0. These as-

sumptions are based on the findings from the Wollert (24), Lunde (17), Schächinger (20), and Janssens (16) articles.

For this evaluation there is a 1:1 active patient to control patient allocation. We assume 5% of patients will be lost to follow-up based on our pilot trial results in 20 patients. From equation (1) the required sample size is 67 patients (rounded up to 68); 34 patients to the day three administration and 34 patients to the day seven administration.

The sensitivity of the sample size to different assumptions about the effect size and standard deviation of the difference are provided (Table 5.)

		Treatment Effect (δ)						
		4 5 6 7						
Std Dev	5	54	35	25	19	15		
of Diff	6	76	50	35	26	21		
(σ)	7	103	67	47	35	27		
	8	134	87	61	45	35		

**Table 5**.Total Sample Size for Effect of Timing on Global Ejection Fraction Type I error = 0.05; power = 80%; followup losses = 5%

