## 3.2.6.3.2 Effect of BMMNC infusion on regional ejection fraction

Assume 80 active group patients and 40 control patients. We are assuming an absolute change  $\delta = 6.5$  and common group standard deviation of the difference of LVEF over time as  $\sigma(\Delta)_{LVEF} = 9.5$  conservatively increased to 10. These assumptions are based on the BOOST manuscript (18, 24). Type I error (two-tailed) = 0.0495. We anticipate 5% of patients will be lost to follow-up. Under these assumptions, the power is 90.4%. A table displaying the sensitivity of the power computation to assumptions concerning effect size and standard deviation of the difference is provided (Table 8).

		Treatment Effect (δ)				
		5	5.5	6	6.5	7
Std Dev	9	0.798	0.868	0.919	0.953	0.975
of Diff	10	0.711	0.791	0.855	0.905	0.941
(σ)	11	0.628	0.711	0.784	0.845	0.893
	12	0.555	0.636	0.711	0.778	0.835
		I				

**Table 8**.Power for the Effect of Dose on Regional Ejection FractionType I error = 0.05; N=120;2:1 active:placebo ratio: followup losses = 5%

A total of 120 patients provide adequate power for an assessment of the overall effect of BMMNC administration to control in the six month change for each of global and regional ejection fraction, as well as permitting an adequately powered inquiry into the influence of timing on the effect of BMMNC for each co-primary endpoint.

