### 9.4.5 Incomplete randomizations

Randomizing patients to the timing of the intervention, separate and apart from their randomization to cell therapy versus placebo therapy, raises the issue of "incomplete randomization," i.e., patients who are randomized to receive 3 day or 7 day administration, but are never randomized to either active or placebo. The impact of a very small number of these patients who are randomized to time but not to cell therapy on the conclusions of the study are negligible. An analysis will be conducted to specifically take these patients into account should their numbers be substantial.

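### The timing question is a therapy-by-timing interaction, but it is sized on the active arms alone, under an equal-placebo premise that sections 8.0 and 9.4.2 undermine

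*Protocol*

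**What the plan says.** Section 1.1 makes the influence of timing on the cell effect the second primary objective. Section 3.2.1 words it as "whether the effect of this BMMNC infusion on regional and global LV function is influenced by whether it is given at three versus seven days". Sections 3.2.6.2.1 and 3.2.6.2.2 define delta as a difference in treatment effects, and the first describes the evaluation as "comparing the effect of BMMNC at the day three administration to the effect of BMMNC at the seven day administration". For the secondary endpoints, section 3.2.3 names the interaction outright: "The interaction of the effect of therapy and timing of administration will be examined with each of the following secondary endpoints".

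Section 3.2.6.2 then states a premise, that "there will be no difference in the response of the control group to either day three or day seven placebo administration". From it the section concludes that the timing evaluation "involves a comparison of the response of the seven day administration active group to the three day administration active group". The resulting totals are 67 (rounded to 68) for global and 80 for regional ejection fraction, at 80% power. Sections 3.2.6 and 3.2.6.3.2 conclude that 120 patients suffice, "permitting an adequately powered inquiry into the influence of timing on the effect of BMMNC for each co-primary endpoint".

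Two other sections bear on the premise. Section 8.0 says that global and regional function often keep improving from Day 3 to Day 7, that this would bias the Day 7 group, and that all patients therefore have a Day 3 baseline MRI. Section 9.4.2 compares the six-month MRI with the Day 3 MRI in the Day 3 arm and with the Day 7 MRI in the Day 7 arm.

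**The concern.** The objective is a difference between two differences: (active minus placebo at Day 7) minus (active minus placebo at Day 3). The contrast used for sizing equals this only if the two placebo arms change by the same amount. Under section 9.4.2, recovery that happens between Day 3 and Day 7 without any cell effect counts as change in the Day 3 arm and is absorbed into the baseline in the Day 7 arm. Active Day 7 versus active Day 3 carries that shift with it. Only the placebo arms can remove it.

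Two errors of interpretation are at stake. The active-only contrast can show a baseline shift as a timing effect, or hide a real advantage of later delivery. And a null interaction could be read as adequately powered evidence that timing does not matter. Section 2.1.4 says that the trial is meant to establish delivery times for a later Phase III study.

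**Working it through.** **Inputs, all from the protocol.** Two-sided alpha 0.05 (3.2.6.1); power 80% and loss 5% (Tables 5 and 6); global delta 5, SD 7 (3.2.6.2.1); regional delta 6.5, SD 10 (3.2.6.2.2); 40 active and 20 placebo patients at each day (Table 4). After 5% loss the cells are 38, 38, 19 and 19.

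**1. The plan's own figures.** Equation (1) with k = 1 is N = 4·SD²·(1.960 + 0.842)² / (0.95·delta²).
- Global: 4 × 49 × 7.849 / (0.95 × 25) = 64.8, or 66 with rounding per arm. The plan says 67.
- Regional: 4 × 100 × 7.849 / (0.95 × 42.25) = 78.2, or 80 with rounding per arm. The plan says 80.

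Both reproduce, to within about two patients.

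**2. Active-only power at the planned size.** SE = SD × √(2/38) = 0.2294 × SD.
- Global: SE 1.606; 5/1.606 = 3.113; power Φ(3.113 − 1.960) = 87.6%.
- Regional: SE 2.294; 6.5/2.294 = 2.833; power Φ(2.833 − 1.960) = 80.9%.

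For global ejection fraction the stated 80% belongs to 34 + 34 patients, not to the 40 + 40 actually planned.

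**3. Interaction from all four cells.** SE = SD × √(1/38 + 1/38 + 1/19 + 1/19) = 0.3974 × SD.

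| | SE | delta/SE | Power | Detectable difference at 80% power (2.802 × SE) |
|---|---|---|---|---|
| Global | 2.78 | 1.798 | Φ(−0.162) = 43.6% | 7.8 |
| Regional | 3.97 | 1.636 | Φ(−0.324) = 37.3% | 11.1 |

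A t reference with 110 degrees of freedom gives 42.9% and 36.8%. With no losses the figures are 45.4% and 38.9%. With the unrounded regional SD of 9.5, power is 40.6%. The detectable differences exceed the whole cell-versus-placebo effects assumed in section 3.2.6.3 (5 and 6.5).

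For scale, 80% power on the interaction at 2:1 allocation needs 18·SD²·7.849 / (0.95·delta²), about 292 patients (global) or 352 (regional).

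**4. What unequal placebo change does to the active-only test.** The protocol gives no size for the difference, so a range of 1 to 4 points is assumed here. With no true interaction and a placebo difference b, the rejection rate is Φ(b/SE − 1.96) + Φ(−b/SE − 1.96), using the SE from step 2.

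| b (assumed) | 1 | 2 | 3 | 4 |
|---|---|---|---|---|
| SD 7 | 10% | 24% | 46% | 70% |
| SD 10 | 7% | 14% | 26% | 41% |

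The nominal rate is 5%.

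**5. Whether the placebo arms can confirm the premise.** With 19 against 19, SE = SD × √(2/19) = 0.3244 × SD. The 95% interval for the placebo difference is ±1.96 × 2.27 = ±4.5 points (global) and ±1.96 × 3.24 = ±6.4 (regional), close to the deltas themselves. A non-significant placebo difference would not establish equality.

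**The case against.** The strongest reply is that nothing was miscalculated. Section 3.2.6.2 declares its premise and derives the contrast from it. If placebo change is equal, active Day 7 minus active Day 3 is the difference in treatment effects, and the sample sizes follow. This stands. A reader might infer that the true power is 44% where the plan says 80%, but those figures belong to different tests, and the 44% and 37% apply only when the placebo difference has to be estimated.

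Next, the baseline conflict is the main cause. If the Day 3 baseline of section 8.0 governed, both placebo arms would be measured over the same interval, the premise would be more plausible, and the active-only power would largely stand. This also stands, and it is why the fix starts there. But section 9.4.2 currently prescribes otherwise.

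It can also be said that the active-only contrast appears only in the sizing text, and that a statistical analysis plan not shown may specify the interaction. That is possible, but it would not repair the power claim, which the protocol itself makes.

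Three stronger readings are not supported:
- **That placebo changes differ by construction.** Section 8.0 says recovery often continues and gives no amount. They are expected to differ, by an unknown amount.
- **That drop-out between timing assignment and infusion makes the active groups non-comparable.** Section 9.4.5 allows for "patients who are randomized to receive 3 day or 7 day administration, but are never randomized to either active or placebo", but treats a very small number as negligible and promises an analysis if there are many. Section 4.3 randomises only patients eligible for both days. No loss rate by timing arm is given.
- **That the timing delta has no basis because, in the earlier trials, "timing was never integrated into the randomization scheme".** Sections 2.1.2 and 2.1.3.6 report non-randomised timing patterns from a meta-analysis and from a subgroup of one randomised trial, and the four sources credited for delta cannot be checked here.

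**Conclusion.** The point holds as an unsupported premise, not as an arithmetic error. The claim of adequate power for timing depends on equal placebo change at the two days, and the protocol's own account of recovery and its choice of analysis baselines make that equality unlikely. Without the premise, power for the stated objective is about 44% (global) and 37% (regional), against about 88% and 81% for the active-only contrast at the same 120 patients. These figures rest on the plan's deltas and SDs, a common SD in all four cells, 5% loss and the 2:1 allocation. The size of the placebo difference, and so of any bias, cannot be determined from the protocol. The comparison of cells with placebo is not affected: its stated power of 94.9% and 90.4% reproduces.

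**What to change.** 1. **Sections 8.0 and 9.4.2:** reconcile the baseline, so that one rule defines the change variable for the Day 7 arm. Section 6.3 already provides a Day 3 MRI for every patient, so a common baseline needs no new scan.
2. **Section 9.4.2:** state that the timing test for each co-primary endpoint is the therapy-by-timing interaction, estimated from all four cells.
3. **Sections 3.2.6, 3.2.6.2.1, 3.2.6.2.2 and 3.2.6.3.2:** replace the claim of adequate power for timing. Suggested text: *With 120 patients and 5% loss, the therapy-by-timing interaction has about 44% power for a difference in effects of 5 points in global ejection fraction (SD 7) and about 37% for 6.5 points in regional ejection fraction (SD 10). The differences detectable with 80% power are about 7.8 and 11.1 points. The 80% figures in Tables 5 and 6 hold only for active Day 7 versus active Day 3, if placebo change is equal at both days.*
4. **Supportive analysis:** keep active Day 7 versus active Day 3 on the common Day 3 baseline, shown beside placebo Day 7 versus placebo Day 3 with its confidence interval. Do not use a non-significant placebo difference as licence to drop the placebo arms.

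The cost is a less favourable stated power for a primary objective. No patients are added, and the total of 120 and the main-effect power stay as they are.
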